The KPC survey is a relatively rapid, low-cost methodology that can provide information quickly, allowing health managers at various levels of the health system to work with other stakeholders such as community members, local authorities, and finance authorities in order to make decisions based reliable information. KPC surveys provide the desired flexibility that allows measurement of differential burden of disease up to the desired level of disaggregation (e.g., district level, community level). Information from a KPC survey provides a basis for tailoring interventions so that they reach the community (coverage) and for assessing their effectiveness toward reducing morbidity and mortality in the long run. These surveys are meant to complement other forms of information collection, such as qualitative studies, to understand why services are not reaching communities or why healthy behaviors are not being practiced. This household survey can be part of a regular monitoring and evaluation system. Questions have been harmonized with the DHS and MICS where appropriate.

We expect to conduct the KPC survey as requests arise in the 24 USAID priority countries (identified by USAID's Office of Health, Infectious Disease and Nutrition) that are the focus of the MCSP.⁹ Surveys may also be implemented in additional countries as requested by USAID missions. This protocol focuses on using the KPC modules to tailor household surveys for use in a variety of maternal and child survival programs in different countries.

⁹ The 24 priority countries are Afghanistan, Bangladesh, Democratic Republic of Congo, Ethiopia, Ghana, Haiti, India, Indonesia, Kenya, Liberia, Madagascar, Malawi, Mali, Mozambique, Nepal, Nigeria, Pakistan, Rwanda, Senegal, South Sudan, Tanzania, Uganda, Yemen, and Zambia.

3. Study Design

The study consists of a cross-sectional household survey to collect knowledge, practice, and coverage information on maternal, child survival, reproductive health, and gender interventions from mothers and/or fathers of children under 5 years of age and/or from women ages 15–49 years and/or men ages 15 years and older. These surveys will be done at different time points during project life cycles in order to measure changes over time. Anthropometric information from children under 5 years of age whose mother is interviewed will be collected.

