The KPC surveys will be implemented in the 24 priority countries where the USAID-funded MCSP will have a presence as well as other countries where in-country USAID missions buy into MCSP to conduct these studies. This generic protocol will have JHSPH (Johns Hopkins Bloomberg School of Public Health) as the IRB of record; the MCSP consortium partner IRBs (JSI [John Snow International], PATH, PSI [Population Services International]) will receive the final approved version. Country-specific plans detailing the sampling and procedures will be added to this generic protocol as "annexes"; this will be done through submitting amendments of the generic protocol to JHSPH's IRB, reflecting any relevant changes that will be made in order to maintain the annexes added as subsets of the generic protocol.

The KPC is a flexible survey tool that can be tailored for various technical areas and combination of areas while maintaining standards for collection of information for specific interventions. For example, all programs that include control of diarrheal disease will collect information about the percentage of children who had diarrhea in the two weeks preceding the survey, were given oral rehydration solution (ORS), and were given zinc. However, programs that do not focus on diarrhea will not collect information on treatment of diarrhea.

KPC surveys will be repeated at various times during MCSP program implementation in a target country, from annually to every 2–3 years. In most cases surveys will be implemented only in MCSP intervention areas, but if the opportunity exists surveys may also be carried out in comparison areas. Specific details for each country conducting a KPC survey will be added as an annex to this generic protocol.

Justification of Sample Size

In order for the KPC to be adapted to what is needed for specific studies, the design provides for limited choices regarding sampling methodology, household selection, respondent selection, and sample size. Each study amendment will specify which options were chosen to be implemented in the individual study.

Sampling Methodologies

The following are the three options for sampling methodology, each of which can be implemented with or without parallel sampling. All sampling methodologies will include a step of choosing clusters.

- 1. 30-cluster, with number of interviews conducted per cluster varying from 7-30
 - a. Parallel sampling
 - b. Without parallel sampling

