- 2. LQAS (lot quality assurance sampling), minimum of 19 interviews per supervision area, minimum of 5 supervision areas
 - a. Parallel sampling
 - b. Without parallel sampling
- 3. Stratified random sampling
 - a. Parallel sampling
 - b. Without parallel sampling

Choosing Clusters

Clusters will be determined by probability proportion to size (PPS). The definition of a cluster may vary country to country. In most cases clusters will be communities in rural areas and neighborhoods in urban areas; however, alternative divisions of populations may be used if appropriate to the country setting. The following are the steps for PPS:

- 1. Create a list (ordered randomly) of communities (or other appropriate division), the population for each, and the total population of all communities (estimates are fine).
- 2. Calculate the cumulative population of each community by summing the total population of the community with the combined total population of all the preceding communities on the list.
- 3. Determine the sampling interval by dividing the total population of the entire program area by the total number of clusters, which is 30 for a 30-cluster survey, a minimum of 95 for LQAS, and a minimum of 96 for stratified.
- 4. Choose a random number to identify the starting point on the list to begin selecting clusters. The random number must be less than or equal to the sampling interval.
- 5. Beginning with the random number, use the sampling interval to identify communities for the clusters (30, 96, or 95).

Household Selection (within a Cluster)

The following are options for household selection.

- 1. In the field, at the time of conducting interviews
 - a. "Spin the bottle"
 - b. Mapping
- 2. With a pre-existing list

In all cases larger clusters should be subdivided before beginning household selection. For urban areas in particular, selection rules must be developed ahead of time on how to handle different housing types, such as high rises or multiple families living in a single dwelling. "Spin the bottle" and mapping are applied at the time of data collection, while using a pre-existing list involves household selection before beginning data collection in the field. For "spin the bottle," the interview team selects the center of the cluster and spins the bottle to determine which direction to go for interviews. Households are selected based on a set (*k*th) interval of households from the center or the nearest neighbor's door.

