For studies that interview women and/or men ages 15–17 years, consent will be obtained from an adult in the household to conduct the interviews or, in the case of emancipated minors (according to local legal definition), they will give their own consent.

Households within each sampled cluster will be visited by the data collectors. Interviewers will ask to speak to an adult (18 years of age or whatever the local legal age of majority is), and if available the interviewers will ask screening questions (and fill out a screening form) to determine whether an eligible mother or father is present in the household. The screening form will be destroyed at the end of the fieldwork. If the answer is yes, and he or she is home and he or she agrees to participate following an informed consent/assent process, then he or she is interviewed. If he or she is not home but expected back within 30 minutes, the interview team will return to the house no more than three times before finishing all the interviews in the area. If unavailable, he or she will be counted as "Non-response" and substituted with someone from another household.

When no eligible mother or father is available in a household, then the interview team proceeds to the next house selected to be visited. If a mother has more than one child age 0–59 months, normally they will be asked about the youngest child. However, for some countries, it can be predetermined to select one of the mother's children at random.

Sample Size Determination

Specific sample sizes will vary from country to country. However, sample sizes will be calculated to provide estimates with confidence levels of 95 percent and precision of 10 percent for key indicators. For stratified random sampling and LQAS the design effect is 1. For 30-cluster sampling a design effect of 2 will be assumed. For all cases, if indicators are to be disaggregated, the total sample size must be multiplied by the number of disaggregation categories; if parallel sampling is needed the sample size must be increased to ensure adequate sample sizes for all indicators collected. Final sample sizes will be powered on the most important indicators, which may result in wider confidence intervals for a few of the other indicators.

For individual studies, decisions will be made regarding the most important indicators for which to collect information. The sample size will be powered for these indicators. After this the study will use the

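### Splitting one 30-cluster survey by district multiplies the interviews but not the clusters, so the stated 10-point precision per district is not assured

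*Protocol*

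**What the plan says.** Protocol, section 3, Sample Size Determination, sets the target: "sample sizes will be calculated to provide estimates with confidence levels of 95 percent and precision of 10 percent for key indicators". It adds that "For 30-cluster sampling a design effect of 2 will be assumed", with no link to the number of interviews per cluster. The rule for subgroups, stated to apply in every case, is that "if indicators are to be disaggregated, the total sample size must be multiplied by the number of disaggregation categories". Step 6 of the list closing that section repeats the adjustment. Neither place mentions clusters.

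Under Choosing Clusters, the sampling interval is found by "dividing the total population of the entire program area by the total number of clusters, which is 30 for a 30-cluster survey". Under Sampling Methodologies, the option reads "30-cluster, with number of interviews conducted per cluster varying from 7-30".

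Section 2, Background and Rationale, says KPC surveys can measure differences in disease burden "up to the desired level of disaggregation (e.g., district level, community level"). Choosing Clusters says what a cluster usually is: "In most cases clusters will be communities in rural areas and neighborhoods in urban areas".

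**The concern.** The rule holds the design effect at 2 for any kind of category. That is reasonable for categories found in every cluster. It is not safe for areas, because an area contains only some of the clusters. Multiplying the total by the number of districts then piles more interviews into the same few clusters of each district, and interviews from one cluster are correlated. Precision per district depends mainly on how many clusters the district has, and the rule leaves that number unchanged.

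At stake are district coverage figures meant to guide local program decisions. A country team that follows the rule as written could quote 10-point precision for each district when the sample gives less. A community-level figure would usually rest on one cluster.

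**Working it through.** **Inputs.** From the protocol: z = 1.96, p = 0.5, target half-width d = 0.10, design effect 2, 30 clusters, 7 to 30 interviews per cluster. The worked example in Sample Size Determination uses a base of 210, which is 30 × 7. The ICC is not given, so it is an assumption here and a range is shown.

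**The protocol's own figures.** N = 1.96² × 0.5 × 0.5 / 0.10² = 96.04, or 96; times 2 gives 192. Both reproduce. So does the two-phase size: (1.96 + 1.28)² × 0.5 / 0.2² = 131.2, and 2 × 131 = 262.

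**Implied ICC.** The design effect is 1 + (m − 1) × ICC, with m interviews per cluster. Setting it to 2 gives ICC = 1/(m − 1):

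- m = 192/30 = 6.4: 0.185
- m = 7: 0.167
- m = 30, the largest permitted take: 0.034

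**Categories that cut across clusters** (age, illness, sex). Each category still gets 6.4 interviews from each of 30 clusters, the design effect stays at 2, and the half-width is 1.96 × √(0.25 × 2/192) = 10.0 points. The rule works.

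**k districts of similar size.** Each has n = 192 (or 210) interviews in about 30/k clusters, so m = n × k/30. The half-width is 1.96 × √(0.25 × deff / n). For k = 2 and n = 210 at ICC 1/6: m = 14, deff = 1 + 13/6 = 3.17, half-width 12.0 points.

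| ICC | Base n | k = 2 | k = 3 | k = 4 |
|---|---|---|---|---|
| 0.185 | 192 | 12.6 | 14.8 | 16.7 |
| 0.167 | 210 | 12.0 | 14.1 | 15.9 |
| 0.10 | 210 | 10.3 | 11.7 | 13.0 |
| 0.05 | 192 | 8.9 | 9.8 | 10.6 |
| 0.034 | 192 | 8.4 | 9.0 | 9.6 |

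With few clusters, a t multiplier on 30/k − 1 degrees of freedom is the more honest one. At base 192 it gives 13.8, 17.1 and 20.4 points at ICC 0.185, and 9.2, 10.4 and 11.8 at ICC 0.034. (For the undivided survey at ICC 0.185 it gives 10.4.)

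**Can more interviews repair it?** With unlimited interviews per cluster, the half-width falls only to 1.96 × √(0.25 × ICC / (30/k)). At ICC 0.185 that is 10.9 points for k = 2 and 15.4 for k = 4.

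**The cap on interviews.** 30 × 30 = 900. Five districts at 192 need 960, or 32 per cluster, so the rule cannot be followed from k = 5. At the two-phase size of 262, four districts already need 1,048.

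**One community.** With 7 interviews the half-width is 1.96 × √(0.25/7) = 37.0 points; with 30 it is 17.9. Ten points needs 96 interviews. A community that is not sampled has no estimate.

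**The case against.** The strongest reply is that no section tells a team to run one 30-cluster survey over several districts and report each to 10 points. The rationale describes KPC surveys in general and attaches no precision to any level. The opening objective allows the program area to be a district itself, in which case all 30 clusters lie inside it. LQAS (at least 95 clusters) and stratified sampling (at least 96) are also on offer, and country annexes make the choice. The only worked multiplication, 4 × 210, concerns child age groups, where the rule is sound. All of this stands, and it narrows the point to a single 30-cluster survey divided by area.

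The reply also notes that the ICC is unknown. A design effect of 2 at 7 interviews per cluster implies a high ICC, whereas the protocol applies 2 across 7 to 30. That stands too: at ICC 0.034 to 0.05, two or three districts meet 10 points on the normal multiplier.

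Deferral to the annexes does not remove the problem. The annexes choose among options bound by this rule, and nothing in the protocol tells their authors to add clusters or to recompute the design effect.

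**Conclusion.** The point holds in a conditional form. When one 30-cluster survey is disaggregated by area, each of k similar-sized districts rests on about 30/k clusters and the stated 10 points are not assured. At the ICC implied by the protocol's own 192/30 or 210/30, the half-width is about 12 to 17 points for two to four districts. At ICC 0.10 it is about 10 to 13, and at 0.034 to 0.05 about 8 to 11. These figures assume p = 0.5 and districts of similar size; a smaller district would have fewer clusters and do worse.

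A reader might infer three stronger claims that the documents do not support:

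- That disaggregation fails in 30-cluster surveys generally. Age, illness and sex categories are unaffected, as are LQAS, stratified sampling and a separate 30-cluster survey per district.
- That districts always miss 10 points. That depends on an ICC the protocol does not give.
- That community results are impossible. A sampled community can be estimated, but only to between about 37 and 18 points.

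No stated sample size is miscalculated. The fault lies in the scope of the rule.

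**What to change.** In Choosing Clusters, Sample Size Determination and step 6 of its closing list, add that for geographic categories under the 30-cluster option one of two things is done:

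- **(a)** Recompute the design effect as 1 + (m − 1) × ICC at the interviews per cluster actually used within the district, with the assumed ICC stated, and report the resulting wider precision. This costs only wording.
- **(b)** Spread the same k × 210 interviews over about 30 clusters of 7 in each reporting district, with a separate sampling interval for each. At ICC 1/6 the design effect returns to 1 + 6/6 = 2 and the half-width to 1.96 × √(0.5/210) = 9.6 points. The interview count does not change; the cost is extra travel.

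In Background and Rationale, limit the community-level wording so that it does not imply 10-point precision. This too is wording only.

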appropriate sample size formula based on the chosen sampling methodology. The value of p (proportion) should be .5 (50%) given that these surveys collect information from a variety of indicators with varying proportions in a population, many of which may not be known before the survey is implemented. A p value of .5 gives the maximum sample size needed to estimate any level.

The sample size for a single survey designed to estimate levels at one point in time (not compared with another group) will be determined by the following:

For stratified sampling, simple random sampling, and LQAS:

$$N = Z\alpha^2 pq / d^2$$

- $Z\alpha = 1.96$ corresponding to a confidence level of 95%
- p = 0.5 (maximum sample size)
- q = 1 0.5 = 0.5
- d =accuracy desired = 10% = 0.10
- $N = (1.96)^2 \times 0.5 \times 0.5 / (0.10)^2 = 96$

For 30-cluster sampling, samples size collected from the preceding formula will be multiplied by 2:

$$N_C = N \times \text{deff}$$

Thus, $N_C = 192$

The number of households visited will be calculated based on estimates of the percentage of families expected to have children in the needed age groups. For example, if it is estimated that 45 percent of households have children 0–23 months and 166 eligible mothers must be interviewed, then survey teams may have to visit N_1 =166 × (100 / 45) = 369 households.

Sample sizes for comparison of two phases or groups will use the following formula for stratified random sampling or simple random sampling:

$$N_1 = N_2 = [Z\alpha_{1/2} + Z\beta]^2 [2pq] / (p1 - p2)^2 = [1.96 + 1.28]^2 [2(.5)(.5)] / (.2)^2 = 1.31$$

- N_1 = baseline sample size
- N_2 = final evaluation sample size
- $Z\alpha_{/2}$ is the Z value corresponding to the chosen level of risk α . ($Z\alpha_{/2}$ should be used in two-sided tests, and $Z\alpha$ should be used in one-sided tests.)
- $Z\beta$ is the Z value corresponding to the chosen level of risk β (it directly relates to the "power" of the test as power = 1β ; ($Z\beta$ = 1.28 for a power of .9)
- p_1 is the expected coverage at baseline (can be set to .5 for maximum sample size)

•
$$q_1 = 1 - p_1$$

• p_2 is the expected final coverage (can be set to .5 for maximum sample size)

•
$$q_2 = 1 - p_2$$

- $p = (N_1 p_1 + N_2 p_2) / (N_1 + N_2)$
- q = 1 p

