For 30-cluster, the final value calculated from the preceding formula is multiplied by 2 (design effect) for a sample size of 262. If it is estimated that 45 percent of the households will have eligible mothers, then the total number of household that must be visited is $N_{1\ell} = N_{2\ell} = 262 \times (100 \ / \ 45) = 582$

Next, if cluster sampling methodology is used, a decision will be made to either to increase the total number of interviews in order to disaggregate into the needed age and illness groups of the children or to use parallel sampling. For example, if information is needed on exclusive breastfeeding of children 0-5 months of age and immunization coverage of children 12-23 months, the sample size as determined by the formula could be multiplied by 4 in order to have enough children 0-5 months to provide exclusive breastfeeding estimates with confidence levels of 95 percent and precision of 10 percent. So, if the original estimate is 210 then the actual sample size will be 840 (4 × 210). However, if parallel sampling is used, then 210 mothers of children 12-23 months and 210 mothers of children 0-5 months should be interviewed for a total of 420 mothers interviewed. In this case it is only necessary to multiple the *n* calculated from the sample formula by 2.

Parallel sampling is especially useful for cluster sampling when information is needed about indicators with different denominators, such as for the following:

Indicator	Denominator
Exclusive breastfeeding of children 0–5 months	Children 0–5 months
Immunization coverage of children 12–23 months	Children 12–23 months
Decision making of mothers	Mothers
Decision making of fathers	Fathers

If LQAS or stratified random sampling methodologies are used, parallel sampling must be used if information is collected for indicators from different age and illness categories of children.

Specific studies will arrive at sample sizes though the following steps. Decisions made will be part of individual study protocols. The steps are as follows:

- 1. Decide on most important indicators.
- 2. Choose appropriate sample size formula.
- 3. Use p = .5.
- 4. Calculate sample size based on appropriate formula.
- 5. If using cluster methodology, decide between inflating the total sample size to allow disaggregation into appropriate age and illness groups or using parallel sampling.
- 6. Adjust the calculated sample size number by needed disaggregation or to collect parallel samples.

For Anthropometry

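### The two-phase sample-size rule wrongly allows p1 and p2 each to be set to .5, and never names the 20-point difference behind its 131/262 as the change to be detected

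*Protocol*

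**What the plan says.** The block is in the protocol, section 3 (Study Design), under Sample Size Determination. Its scope sentence reads: "Sample sizes for comparison of two phases or groups will use the following formula for stratified random sampling or simple random sampling". The formula has (p1 − p2)² in the denominator and is worked through as "1.96 + 1.28]^2 [2(.5)(.5)] / (.2)^2 = 1.31". The key gives Zβ as "1.28 for a power of .9".

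The key then describes the two coverages. Of p1 it says that it "is the expected coverage at baseline (can be set to .5 for maximum sample size"), and of p2 that it "is the expected final coverage (can be set to .5 for maximum sample size"). The pooled p is defined separately, as the average of p1 and p2 weighted by the two sample sizes.

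For 30-cluster surveys the result "is multiplied by 2 (design effect) for a sample size of 262", and 582 households follow at 45% eligibility. The six numbered steps that close the section fix p at .5. None of them asks for the difference to be detected.

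**The concern.** All three secondary objectives are to measure changes (in knowledge, in practices and care-seeking, and in coverage), and the Study Design section says that surveys are repeated for that purpose. The two-phase formula is therefore the sizing rule for those objectives. Two things look wrong in it.

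- The advice on p1 and p2 treats them like the single p of the one-survey formula, where .5 does give the largest N. In the two-phase formula they also fix the difference in the denominator, so choosing them for convenience changes the effect size.
- The difference drives N more than any other input, yet it appears only as a number inside a worked line. The stated target of 95% confidence and 10% precision concerns estimating a level, not detecting a change.

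This is a generic protocol whose options and formulas are taken up in country annexes, so a faulty rule can carry into each repeat survey. A baseline round that was sized too small cannot be enlarged later.

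**Working it through.** **Inputs, all from the block:** Zα/2 = 1.96; Zβ = 1.28 (power .9); pooled p = q = .5; difference .2; equal sizes per round; design effect 2 for 30-cluster.

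**1. The protocol's own figure.** N = (1.96 + 1.28)² × 2 × .5 × .5 / .2² = 10.4976 × .5 / .04 = 131.22, so 131 per round. Then 131 × 2 = 262, and 262 × 100 / 45 = 582. Both later figures reproduce. The printed 1.31 does not; it is 131 with a misplaced decimal point.

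**2. Both coverages at .5.** p1 − p2 = 0, so the formula divides by zero and N is undefined.

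**3. One coverage at .5.** Take, as an assumed illustration, an expected rise from 30% to 40%.

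- As expected: pooled p = .35, difference .10. N = 10.4976 × 2 × .35 × .65 / .10² = 10.4976 × .455 / .01 = 477.6, so 478.
- With p2 moved to .5: pooled p = .40, difference .20. N = 10.4976 × 2 × .40 × .60 / .20² = 10.4976 × .48 / .04 = 126.0, so 126.

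The note promises the maximum sample size and here delivers about a quarter of the size needed (126 / 478 = .26).

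**4. What 131 per round can detect at average coverage near 50%.** Power = Φ(d / √(2pq / n) − 1.96), with 2pq = .5 and n = 131, so √(.5 / 131) = .0618. The same powers apply to 262 with design effect 2. N for 90% power is 10.4976 × .5 / d².

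| Change d | Power at 131 (262 with design effect 2) | N per round for 90% power, design effect 1 / 2 |
|---|---|---|
| 20 points | 90% | 131 / 262 |
| 15 points | 68% | 233 / 467 |
| 10 points | 37% | 525 / 1,050 |

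**5. How far this depends on p = .5.** The change detectable with 90% power at 131 is 3.24 × √(2pq / 131). At average coverage .8 this is 3.24 × √(.32 / 131) = .16. At .9 it is 3.24 × √(.18 / 131) = .12.

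**6. LQAS.** The single-survey formula names LQAS, and the section gives LQAS a design effect of 1. The two-phase formula names stratified and simple random sampling, and the next paragraph adds 30-cluster. LQAS is one of the three permitted designs, but the block does not say how to size it for a comparison.

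**The case against.** The strongest reply is that the block works. The protocol itself applies it with pooled p = .5 and a separate difference of .2, and carries 131 forward correctly to 262 and 582. The general text and the six steps already place .5 on p. The notes say only that p1 and p2 may be set to .5, and anyone who set both would hit a division by zero at once. Annexes must also submit their own sampling details as amendments.

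Much of this stands, and it rules out several stronger readings.

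- A reader might infer that the formula cannot be used. The worked example shows that it can.
- A reader might infer that the effect size is concealed. The .2 and the power of .9 are both printed; what is missing is a sentence naming .2 as the detectable change and a step for choosing it.
- A reader might infer that 131 gives 90% power only for 20 points. That holds near average coverage of 50%, the least favourable case; at .9 about 12 points suffices, and larger changes have more power.
- A reader might infer an arithmetic error that spreads. Nothing later depends on 1.31, and it may be an artefact of text extraction, since other characters in the block, such as the minus sign in q, are missing too.
- A reader might infer that LQAS comparisons are planned at 95 per round, or other comparisons at 96 or 192, with power below 90%. But 95 (5 areas × 19 interviews) is a minimum, and 96 and 192 are expressly for surveys not compared with another group.

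The reply does not rescue the notes on p1 and p2. Setting only one of them to .5 gives no visible failure, just a different and possibly much smaller N.

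**Conclusion.** The notes on p1 and p2 state a sizing rule that is wrong. Followed for both, they give no N; followed for one, they can cut N from 478 to 126 in the assumed 30%-to-40% case. That case is an illustration, not a figure from the protocol, and the direction and size of the error depend on which coverage is replaced and on the true values.

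The 131/262 figures are correct for their inputs but lack a statement of what they detect: 90% power for 20 points, falling to 68% for 15 and 37% for 10. These powers assume average coverage near 50%, a two-sided 5% test, equal rounds and, for 262, a design effect of 2.

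The printed 1.31 is at most a decimal slip with no effect on later figures. The block's silence on LQAS is a gap to close, not evidence that any LQAS survey is undersized.

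**What to change.** 1. Delete both notes that allow p1 and p2 to be set to .5. Say instead that the pooled p may be set to .5 (for example p1 = .40, p2 = .60), and that p1 − p2 is the smallest change to be detected and must be stated in each annex. Add a step for choosing it to the six sizing steps.
2. State that 131 per round (262 for 30-cluster with design effect 2) gives 90% power for a 20-point change at average coverage near 50%, and about 68% for 15 points and 37% for 10 under the same condition.
3. Check the printed 1.31 against the source file and print 131.
4. State whether the two-phase formula, with design effect 1, also applies to LQAS surveys used to measure change. Do not present the LQAS minimum of 95 as the comparison size.

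The cost is protocol wording. No figure carried forward changes and the correction itself adds no interviews. An annex that chooses to detect less than 20 points near 50% coverage would need a larger sample, as the table shows.
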